Data will be coded on two levels. Each subject will be given a unique code according to their primary assignment. When data is entered, it is entered in numerical form, eg (Yes=1, No=2). The data code is kept separate from the data, which would make the raw data uninterpretable otherwise.

Data that is entered through the online diaries through either SurveyMonkey or REDCap will be entered with the subject’s code, not their real name. No personally identifying information will be ascertained on the questionnaires. SurveyMonkey procedures allow for creation of a study specific research.net URL that only subjects within the study can ascertain. REDCap is an online electronic data capture program (project-redcap.org) used by over 600 institutions for anonymous data capture. As the study grows in scope, either one of these sites may be used. No personally identifying information is stored on either of these sites. The link to access the sites are, however, sent to the subject via their email address. If the

subject does not consent to use of electronic datacapture, they will always be give the option of entering all data on a paper document.

The link to the patient identifications as well as to the encoded data is stored on a password-protected computer on a separate spreadsheet in a locked room. Only [name] will have access to the link. Anonymized data can be requested in writing to the PI. However, there would be no need for any personally identifying information to be revealed to other investigators.

If [name] leaves LIBR, and agreement will be made between LIBR and [name] new institution to transfer the data so that the study can continue. If another investigator at LIBR becomes a co-investigator of the study, their name will be added to the list of investigators and they will become responsible for maintaining data security at LIBR.

Study information will be made available to the subjects when there has been sufficient recruitment to make reasonable aggregate assessments. We can share general study characteristics (how many people were recruited, age, primary disorder etc.) early in the process but we do not share study results with subjects until the quality of the data is close to publication level.

L. Confidentiality

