Title: Transcranial Magnetic Stimulation for Mal de Debarquement Syndrome

Principal Investigator:

[name]

Associate Investigator, Laureate Institute for Brain Research (LIBR), Adjunct Assistant Professor, UCLA School of Medicine

Sponsor:

Laureate Institute for Brain Research, Inc.

Abstract

Mal de débarquement syndrome (MdDS) is a balance disorder in which patients develop a persistent internal sense of movement after a prolonged period of passive motion exposure. This is classically described as "land-sickness" occurring after boat rides. Patients describe a hallucination of movement such as "rocking" and "bobbing" even though they are not physically moving. This disorder is thought to be due to a primary problem of brain adaptation as testing of inner ear function and structural brain imaging is always normal. However, it is unknown which parts of the brain control this adaptation. Most cases of *mal de débarquement* only last a few hours, but there are many people who experience the symptoms for months or years, leading to significant morbidity. The term MdDS is generally reserved for patients who experience symptoms for at least one month.

Our preliminary data on imaging patients with MdDS with FDG PET and functional MRI has shown that there is abnormal metabolism in limbic structures that control spatial processing and emotional regulation in these individuals and that there are also differences in the functional connectivity between these limbic structures and the cortex. We are now working on modulating the perception of motion in MdDS with transcranial magnetic stimulation (TMS), which is a form of external neuromodulation using pulsatile magnetic fields on the surface of the head. Preliminary data shows that TMS can at least temporarily suppress the perception of rocking with short-term treatment. However, long-term studies are needed in order to determine whether the short-term suppression can translate into a remission.

A. Specific Aims

The goal of this study is to determine whether external neuromodulation using rTMS can reduce the perception of self-motion that is experienced by patients with MdDS. We will make correlations between functional MRI data, EEG, and specific clinical features to determine whether functional connectivity between particular hubs in the brain correlate with clinical improvement.

B. Background and Significance

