More options are needed for treating patients with MdDS because they do not respond to the typical therapies given for inner ear disorders. Vestibular therapy and vestibular suppressants are not helpful and sometimes worsen symptoms. Benzodiazepines provide palliation only, and limited data on the use of selective serotonin reuptake inhibitors shows that, though they are helpful in some patients, are not effective in many others. The second hypothesis of this study is that external neuromodulation with transcranial magnetic stimulation can reduce the perception of motion. Expanding the study of MdDS by examining changes in resting state networks, functional connectivity, and response to neuromodulation will change concepts of how vestibular adaptation occurs and can be modified.

C. Preliminary Studies

Neuroimaging: Determination of metabolic activity and functional connectivity differences between individuals with MdDS and healthy controls

We subsequently imaged 20 individuals with MdDS and 20 healthy controls with resting state FDG-PET to show that the left entorhinal cortex/amygdala junction is hypermetabolic in MdDS individuals (**Figure 1**) while prefrontal and temporal cortex areas are hypometabolic (Cha et al PLoSOne 2012).

[figure not shown]

Figure 1: Area of relative hypermetabolism in MdDS subjects compared to controls. Cluster with peak voxel $z > 3.3$ for the MdDS > CTRL contrast (MNI coordinates -14, -8, -22) centered at the entorhinal cortex/amygdala transition shown in A) sagittal, B) coronal, C) axial planes. Image is presented at $z = 2.57$ for better visualization. from Cha et. al. PLoSOne 2012.

The role of the entorhinal cortex in the processing of spatial information appeared to be a plausible factor in why people with MdDS experience spatial disorientation and increased visual motion sensitivity after illness onset. The metabolic differences seen in this study were found after regressing out the effect of high depression or anxiety scores determined through the Hospital Anxiety and Depression Scale (2). However, the decreased prefrontal activity along with amygdala activity may be a partial explanation for why anxiety tends to increase with the onset of symptoms of MdDS.

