Figure 3. Correlation between treatment effect at 60 minutes after 10Hz DLPFC stimulation and duration of illness. Blue circles= score at 60-minutes; red circles =cases in which the maximum change was not at 60-minutes.

The next study was a double-blind sham-controlled study of five sessions of left DLPFC stimulation in eight women with MdDS.

[figure not shown]

Figure 4. Change in Dizziness Handicap Inventory from baseline, immediately after rTMS, and for four weeks post rTMS. Mixed effects repeated measures ANOVA was performed to account for both within subject and between subject variance.

In this study (manuscript in progress) we found that Dizziness Handicap Inventory scores decreased significantly after real rTMS but not after sham rTMS at post TMS weeks 1, 3, and 4 with a trend for improvement at week 2 (**Figure 4**). From a functional standpoint, two of the eight women experienced significant reductions in rocking dizziness for about three months after receiving rTMS. They were able to return to almost all of their regular activities with only minimal symptoms. Two others noted some moderate improvement. Two had no change with either real or sham stimulation, and two were worsened by both kinds of stimulation likely due to the fact that they had to travel by plane to participate in the study. A second group in Australia has also provided evidence that rTMS over DLPFC can improve balance function in MdDS. However, our recent study was the first to show that long-term symptom relief could be achieved with rTMS with improvement that lasted well beyond the treatment period.

In order to determine what biomarkers may be different in responders versus non-responders to rTMS, new collaborators were cultivated in Oklahoma and the subsequent rTMS studies included both resting state fMRI and high-density EEG before and after five days of treatment with a combination of 10Hz left/1Hz right DLPFC rTMS (there was no access to a PET scanner in Tulsa). Our goal was to determine what functional connectivity changes were markers of symptom improvement, markers that could lead to the development of better subsequent targets.

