After determination of motor threshold, the TMS coil will be positioned at predetermined locations over the cortex using frameless stereotaxy as described above. Surface electrodes will be kept over hand muscles on both hands for the purpose of continuous monitoring of the safety of the procedure. We will also use theta bursting TMS (TBS) at inhibitory settings (continuous TBS-cTBS).

Theta burst TMS will be limited to established protocols using 600 pulses per session (40 seconds for cTBS). The first TMS session could last as short as 2 hours and as long as 3 hours with multiple sessions of TBS administered with a break of 30-minutes in between sessions.

Daily rTMS sessions (for MdDS subjects only)

Participants with MdDS will receive one sessions each of 3 different targets: occipital cortex, cerebellar vermis, lateral cerebellar hemisphere. The order in which these sessions will be administered will be randomized between participants. All test sessions will be done on Day 2 (Day 1 will involve baseline fMRI and EEG measurements). The treatment choice will depend a combination of the participant's assessment of which target was a the most effective in reducing the vertigo. If they are not sure, then balance assessment with the SWAY balance app will be used to determine which protocol improved their balance the most.

We plan an enrollment of 24 participants which would provide 4 groups of each of 6 possible orders of stimulation. Participants will be asked to rate the intensity of their rocking vertigo. The goal is to provide up to 12 sessions of rTMS over 3 days with 30-minutes of break in between. The end of the final day of stimulation will include fMRI and EEG.

E. Statistical Methods

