This is a pilot study so there are no set power calculations. The goal is to determine which if any of three rTMS targets are most effective in reducing oscillating vertigo. Pre-stimulation baseline scores will include weekly assessments of the DHI, MBRS, and the HADS divided into the Anxiety and Depression subscores. The median of 4 weekly prestimulation scores will be used as the baseline. The participants will be making immediate post assessments of each of these scores and weekly thereafter for 6 weeks. The differences between these weekly scores and the prestimulation baseline will be calculated. Baseline clinical features that determine target selection will be placed in a one-way ANOVA with one factor and three levels for response groups (occipital target, vermis target, lateral cerebellar target) with post hoc Bonferroni correction to determine which targets showed different responses.

F. Gender/Minority/Pediatric Inclusion for Research

Women and minorities will be included in the study. Prior research indicates that MdDS predominantly affects females, without any predilection for any racial or ethnic groups. It is a disorder of adults, however, as the average age of a first episode is near 40 years old.

G. Human Participants

We plan to enroll 24 subjects with MdDS and 20 healthy controls over a span of 5 years.

Inclusion criteria for controls:

1. Age \geq 18 years old
2. Willing and capable of interacting with the informed consent process
3. No history of dizziness or balance disorder.

Inclusion criteria for MdDS subjects:

1. Age \geq 18 years old
2. Willing and capable of interacting with the informed consent process
3. Primary disorder being a persistent perception of motion with no other cause determined after a careful interview.

Exclusion criteria for both:

1. Subjects who cannot comply with study conditions.
2. Active psychiatric condition such as mania or psychosis
3. Unstable medical condition
4. Implanted metal anywhere in the body (infusion pumps, pacemakers, metal or shrapnel in the body, deep brain stimulators, aneurysm clips, metal prostheses, joints, rods or plates). Dental fillings are acceptable.

5. Personal history of seizures or a first-degree relative with uncontrolled epilepsy

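### Section A says the study will determine whether rTMS reduces perceived self-motion, but with active stimulation only it can compare targets and describe change, not determine that

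*Combined protocol and SAP*

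**What the plan says.** **Aim.** Section A (Specific Aims): "The goal of this study is to determine whether external neuromodulation using rTMS can reduce the perception of self-motion". Section B (Background and Significance) gives as the second hypothesis that "external neuromodulation with transcranial magnetic stimulation can reduce the perception of motion".

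**Treatment.** Section D, Daily rTMS sessions: "Participants with MdDS will receive one sessions each of 3 different targets: occipital cortex, cerebellar vermis, lateral cerebellar hemisphere". On allocation: "The order in which these sessions will be administered will be randomized between participants". The target for the treatment block rests on the participant's "assessment of which target was a the most effective in reducing the vertigo", with the SWAY balance app used if the participant is unsure. Up to 12 sessions over three days are planned. No sham, untreated or delayed-treatment MdDS group appears, and no masking is described.

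**Controls.** Section G plans 24 participants with MdDS and 20 healthy controls. Controls must have no history of dizziness or balance disorder. The rTMS headings in Section D apply to MdDS participants only; controls are mentioned for motor-threshold determination.

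**Analysis.** Section E calls the study a pilot without power calculations and gives a narrower goal: "The goal is to determine which if any of three rTMS targets are most effective in reducing oscillating vertigo". Baseline is the median of four weekly scores. DHI, MBRS and HADS are scored immediately after stimulation and then weekly for six weeks, each as a difference from baseline. The only named test is a one-way ANOVA of baseline clinical features across three target groups, with Bonferroni correction.

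**The concern.** Sections A and B ask an absolute question: does rTMS lower the motion percept compared with not having it? Answering that requires some estimate of what would have happened without active stimulation. The plan has none for people with MdDS. The outcomes are self-rated, and participants know they are choosing the target that seemed best to them.

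What is at stake is the conclusion the trial may draw. If Section A stands, a fall from baseline over six weeks could be reported as the answer to the stated aim, although expectation, attention, travel or natural course could have contributed to it. Section E is closer to what the design can deliver, but its goal still asks whether any target is effective, so it does not settle which conclusion is intended.

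**Working it through.** **1. The plan's own figure.** Three targets have 3! = 6 possible orders. With 4 participants per order, 6 × 4 = 24, which matches the planned enrolment. The figure balances order and provides no comparator: all 24 receive active stimulation, so the number of MdDS participants without it is 24 − 24 = 0.

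**2. What each contrast identifies.** Write the mean change seen with target *k* as τ_k + ν. Here τ_k is the specific effect of stimulating that target, and ν is the non-specific change (expectation, attention, travel, natural course, residual regression to the mean).

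- *Day 2, target j against target k:* (τ_j + ν) − (τ_k + ν) = τ_j − τ_k, if ν is the same for each target. The non-specific part cancels and the order is randomised. This supports a relative, exploratory statement.
- *Six-week change from baseline:* τ + ν. This is one observed quantity with two unknowns, so τ cannot be recovered.
- *Healthy controls:* they have no symptom to reduce and receive no rTMS, so they estimate neither τ nor ν.

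Three equally effective targets and three equally ineffective ones give the same Day 2 contrasts, namely zero. The randomised part of the design therefore cannot answer Section A, and the before-after part is uncontrolled.

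**3. The named test.** The ANOVA in Section E takes baseline clinical features as its input. Its closing words refer to differing responses, but on either reading it compares groups that all received active stimulation and were formed by choice of target. It does not test the Section A aim. Section E names no analysis of the Day 2 rocking ratings.

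**4. Illustration of what an uncontrolled change can produce.** The documents give no SD and no size of non-specific change, so the shifts below are assumptions. The before-after test is also an assumption, since the plan does not specify one. With τ = 0, n = 24 and a non-specific improvement of *s* SDs of the change, a two-sided 5% z-test is significant with probability

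P = Φ(s√24 − 1.96) + Φ(−s√24 − 1.96), where √24 = 4.899.

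| assumed s | s√24 | P |
|---|---|---|
| 0 | 0 | 0.050 |
| 0.2 | 0.980 | 0.165 |
| 0.3 | 1.470 | 0.312 |
| 0.5 | 2.449 | 0.688 |
| 0.8 | 3.919 | 0.975 |

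**5. Choosing the best target.** If three targets are equally ineffective and their ratings are independent normal, the expected maximum is 3/(2√π) = 0.85 SD above the mean. This is a Day 2 figure for the chosen target. It is not a bias of that size in the later weekly scores, which are compared with a separate pre-stimulation baseline.

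**The case against.** The strongest reply is that this is a declared pilot looking for targets. Section C ends by describing a search for better rTMS targets, Section E states the narrower goal, and randomised order suits that goal. No efficacy test or success threshold is set. All of this is correct, and it is why omitting a sham is defensible as a design choice. But the pilot label excuses the missing power calculation, not an aim that the design cannot answer.

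The plan also has real mitigation. A median of four weekly scores lessens regression to the mean. Section B says spontaneous resolution becomes much less likely with longer illness, although Section G sets no minimum duration. Neither removes expectation, attention or travel effects.

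The sponsor's earlier sham-controlled study favours rTMS: DHI fell significantly after real stimulation at weeks 1, 3 and 4, and did not fall significantly after sham. That was left DLPFC stimulation and does not establish efficacy at occipital or cerebellar targets.

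A reader might infer more than the documents support, in five ways:

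- *That half of the earlier participants show what a sham would separate.* Section C reports: "Two had no change with either real or sham stimulation, and two were worsened by both kinds of stimulation". The two who were unchanged would be classed as unchanged with or without a sham. Only the two who worsened are relevant, and the sponsor attributes that to air travel.
- *That the documents show bias towards benefit.* The one non-specific change they describe is worsening, which would count against rTMS.
- *That the sponsor will read every fall as success and every rise as harm.* Nothing says so. In the 10-person series in Section C, three worsened and only one case was attributed to rTMS.
- *That the protocol declares open treatment.* It does not mention masking either way.
- *That a sham session on Day 2 would cure the problem.* It would leave the treatment block and the six-week change uncontrolled. With four conditions sham comes first in 3! = 6 of 4! = 24 orders, so it would follow active stimulation in 18. The only sham the documents report was for left DLPFC.

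**Conclusion.** The point holds as a mismatch between the stated aim and what the design can conclude. Sections A and B promise a determination of efficacy. The design supports an exploratory within-participant comparison of acute ratings between three active targets, and an uncontrolled description of change after the block.

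The size of any resulting error cannot be taken from the documents. The range of 17% to 98% is conditional on assumed non-specific improvements of 0.2 to 0.8 SD, no specific effect, and a before-after test that the plan does not specify. It shows only that a significant fall would not be strong evidence for rTMS.

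As context only, 2 of 8 participants (25%, exact 95% CI 3% to 65%) in the earlier study worsened on both real and sham stimulation. This shows that non-specific change occurs in this population. It does not estimate its size or direction here, because the target and regimen were different.

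**What to change.** Reword Section A, the matching hypothesis in Section B, and the goal in Section E so that the trial's conclusions are limited to two:

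1. An exploratory within-participant comparison of the acute Day 2 rocking ratings across the three active targets given in randomised order. Section E should name this comparison, since at present it does not.
2. A description of the change in DHI, MBRS and HADS from baseline over the six weeks after the treatment block, labelled as uncontrolled, with an explicit statement that it cannot by itself show that rTMS reduces symptoms.

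The cost is a protocol amendment and a more modest claim. Enrolment, schedule, treatment and data collection are unchanged.

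### The Section E groups mix participants placed by perceived vertigo reduction with participants placed by a balance test, and the plan neither records nor separates the two routes

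*Combined protocol and SAP*

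**What the plan says.** Section D (Daily rTMS sessions) gives each MdDS participant one test session at each of three targets on Day 2, in randomized order. The target for treatment is then chosen by a combination whose only named element is "the participant's assessment of which target was a the most effective in reducing the vertigo". The fallback is: "If they are not sure, then balance assessment with the SWAY balance app will be used to determine which protocol improved their balance the most". The next paragraph adds: "Participants will be asked to rate the intensity of their rocking vertigo". It gives no scale or timing for that rating and does not say whether it feeds into the choice.

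Section E states the aim: "The goal is to determine which if any of three rTMS targets are most effective in reducing oscillating vertigo". Its one named test is introduced by "Baseline clinical features that determine target selection will be placed in a one-way ANOVA", and the single factor has "three levels for response groups (occipital target, vermis target, lateral cerebellar target" as its levels. Section E does not distinguish participants by how their target was chosen and plans no sensitivity analysis on that point.

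**The concern.** Two different questions feed one label. A participant who is sure is placed by which target most reduced the vertigo. One who is not sure is placed by which target most improved measured balance. Both are then called responders to that target.

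The two may go together, but nothing in the documents shows that they pick out the same best target. The Abstract describes motion that is felt without physical movement, and Section C reports balance function from another group's work separately from symptom relief.

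The unsure are by definition those who could not name a target that helped the vertigo most. The aim asks which target, if any, is best, but the rule always yields one. If many are placed this way, a link between baseline features and the vertigo-reducing target is blurred. The label also cannot support a statement about vertigo for everyone who carries it.

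**Working it through.** **The plan's own figure.** Three targets give 3! = 6 orders, and 6 × 4 = 24 participants, as Section D states. No figure in the plan is in dispute.

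**How the passages fit together.** That the Section E groups are the targets selected in Section D is an inference. It is a strong one, because the Section E sentence speaks of target selection and its level names match the three test targets.

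**Inputs.** N = 24 comes from Sections D and G. The documents give no share of unsure participants (u), no rate at which SWAY picks the target that is best for vertigo (a), no effect size and no alpha. All four are assumptions below.

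**Formula.** Treat everyone placed by vertigo assessment as correctly placed for vertigo. The share placed correctly overall is then c = 1 − u(1 − a). With three equal groups and the misplaced split evenly over the other two, the expected difference between groups is multiplied by

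(3c − 1)/2 = 1 − 1.5u(1 − a).

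- Chance agreement, a = 1/3: 1 − 1.5u × 2/3 = 1 − u.
- 80% agreement, a = 0.8: 1 − 1.5u × 0.2 = 1 − 0.3u.
- Perfect agreement (a = 1) or nobody unsure (u = 0): 1, so no loss.

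The number placed by SWAY is 24u, and the number misplaced is 24u(1 − a).

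| u (assumed) | Placed by SWAY | Misplaced, a = 1/3 | Difference kept | Misplaced, a = 0.8 | Difference kept |
|---|---|---|---|---|---|
| 10% | 2.4 | 1.6 | 90% | 0.5 | 97% |
| 25% | 6.0 | 4.0 | 75% | 1.2 | 92.5% |
| 40% | 9.6 | 6.4 | 60% | 1.9 | 88% |

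**Illustrative power.** This uses a one-way ANOVA with the noncentral F distribution, N = 24, three equal groups, alpha 0.05 and total variance held fixed. With k the multiplier above, f² becomes f²k²/(1 + f² − f²k²).

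| Assumed f | No misplacement | u = 10%, a = 1/3 | u = 25%, a = 1/3 | u = 10%, a = 0.8 | u = 25%, a = 0.8 |
|---|---|---|---|---|---|
| 0.7 | 0.822 | 0.690 | 0.480 | 0.785 | 0.725 |
| 0.4 | 0.353 | 0.285 | 0.202 | 0.331 | 0.301 |

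**Is a non-trivial u plausible?** Section C offers only a rough guide. In the sham-controlled study, 2 of 8 (25%) had no change with either stimulation. In the ten-person series, five improved and three worsened, which leaves 10 − 5 − 3 = 2 (20%). Those studies used other targets, and having no change is not the same as being unsure which of three targets was best.

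**The case against.** The best defence is that this is an ordinary tie-break in a pilot with no power calculation. The first rule is framed in terms of vertigo, matching the aim, and SWAY applies only when that rule gives no answer. The ANOVA concerns baseline features that go with target selection, and for that question the selected target is the proper factor, however it was reached. Symptom change can also be described from the weekly DHI, MBRS and HADS scores, collected alike in everyone, and Section A plans correlations with imaging and EEG. All of this stands as a defence of the treatment rule and of keeping the selected target as the factor. It does not justify calling that factor response, or leaving the route unrecorded.

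A reader might infer several stronger points that the documents do not support:

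- *That sure participants are placed by a loose general impression, or that the sessions were unblinded.* The text ties the assessment to vertigo. It does not say whether participants know the target being stimulated.
- *That the rocking rating plays no part in selection.* Its role is unspecified. The combination in Section D lacks its other elements, so the rating may inform the choice; equally, it may not be taken for each target.
- *That a balance-based label carries no information on perceived motion.* The Abstract calls MdDS a balance disorder, Section C cites improved balance as evidence for rTMS, and someone unsure between two targets has still ruled out the third.
- *That everyone should be regrouped by the largest fall in rocking rating.* Participants who felt no clear difference would probably have near-tied ratings and be assigned by noise. The analysed group would also part from the treated target, which the six-week scores follow.

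**Conclusion.** The concern holds in a limited form. As written, the Section E factor pools a vertigo-based and a balance-based placement under a response label, while the aim is about vertigo alone. The ANOVA can describe who ended up with which target. It cannot, without further information, be read as describing whose vertigo responded to which target.

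The size is unknown. A reader might take a 10% to 40% dilution as the finding, but that needs both an assumed unsure share in that range and chance-level agreement between SWAY and vertigo. At 80% agreement the same range gives 3% to 12%. With nobody unsure or perfect agreement there is no loss. With groups averaging 24/3 = 8, even a few misplaced participants can matter, and the remedy is cheap enough to adopt without knowing the size.

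**What to change.** Leave the treatment-selection rule with the sponsor, and make four changes to the analysis and data collection.

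1. Keep the selected target as the Section E factor, but name it selected target rather than response.
2. Record for each participant whether the target was selected by vertigo assessment or by SWAY, and report the counts by target.
3. Prespecify a repeat of the ANOVA that excludes participants placed by SWAY, or puts them in a separate category for no clear vertigo difference.
4. Take the already planned rocking-intensity rating immediately before, and at a fixed time after, each Day 2 test session in everyone, and state the scale. Analyse its change by target as the vertigo outcome. Report SWAY change separately as a balance outcome.

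The cost is protocol wording and a few minutes of ratings on Day 2. SWAY should add little: uncertainty is known only after all three sessions, so the fallback already needs balance measured around each one. The sensitivity analysis has smaller groups: at 10% to 40% unsure, 24 × 0.9 = 21.6 down to 24 × 0.6 = 14.4 participants remain. The separate category avoids dropping anyone.
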